Summary Table of Study Protocol

Title	Comprehensive Analysis of Clinical Parameters That May Inform the Choice of Dose Regimen for Carfilzomib 20/27mg/m ² or 20/56mg/m ² With and Without Dexamethasone
Protocol version identifier	20200381 Version 1
Date of last version of the protocol	11 September 2020
EU Post Authorization Study (PAS) Register No	Yes
Active Substance	NA
Medicinal Product	NA
Device	NA
Product Reference	NA
Procedure Number	NA
Joint PASS	Yes
Research Question and Objectives	Evaluate the benefit-risk profile of the clinical parameters that are associated with efficacy and safety outcomes for each carfilzomib dosing regimen (20/27mg/m ² and 20/56 mg/m ²) with or without dexamethasone which may inform the choice of carfilzomib dose
Country(ies) of Study	Global
Author	PPD Amgen Inc Global Clinical Development Thousand Oaks, CA PPD

Marketing Authorization Holder

Marketing authorization holder(s)	NA
MAH Contact	NA

This protocol was developed, reviewed, and approved in accordance with Amgen's standard operating procedures.

Figure 1. Study Design Schema

Step 1: Identify all Amgen acquired or sponsored clinical trial in Onyx-owned or RAVE database until 14 July 2019

[figure not shown]
Step 2: Within those databases, identify clinical trials that enrolled RRMM subjects

- These subjects may have received any number of prior lines of therapy

Step 3: Among those clinical trials, identify all subjects with RRMM treated with K dosing frequency of twice a week at the start of each week for three of the four-week cycles (days 1, 2, 8, 9, 15, 16 for each 28-day cycle) for all cycles of treatment.

Step 4: Separate those subjects based on treatment of K27, Kd27, K56, or Kd56

- If the regimen in the individual clinical trial dictates that the first and/or second cycle of K therapy is 15mg/m² or 20mg/m², but 27mg/m² is specified for subsequent K cycles of therapy, then the clinical trial will be included for subjects who receive K at 27mg/m² with or without dexamethasone.
- If the regimen in the clinical trial dictates that the first cycle of K therapy is 27mg/m², but 56mg/m² is specified for subsequent K cycles of therapy, then the clinical trial will be included for subjects who receive K at 56 mg/m² with or without dexamethasone.
- Therapeutic dexamethasone dosing will be based on The subject receiving at least 20mg per week.

1. Table of Contents

Summary Table of Study Protocol 1

1. Table of Contents 3

2. List of Abbreviations 6

Comprehensive Analysis of Clinical Parameters that May Inform the Choice of Dose Regimen for Carfilzomib 20/27mg/m² or 20/56mg/m² With and Without Dexamethasone

- Study Background and Rationale

Prior attempts to evaluate different carfilzomib (K) and carfilzomib in combination with dexamethasone (Kd) dosing regimens demonstrated limitations of the collected data on clinical parameters and outcomes. The aim of this analysis is to pool data from Amgen-sponsored clinical trials to describe the benefit-risk profile of clinical parameters associated with efficacy and safety outcomes of subjects treated with one of four different dosing regimens to inform the choice of carfilzomib regimen. The dosing regimens of carfilzomib include a therapeutic dose of 27mg/m² or 56mg/m², each as monotherapy or in combination with dexamethasone (K27, K56, Kd27, Kd56).

- Study Feasibility and Futility Considerations

Upon initial review of Amgen-sponsored K clinical trials, there was a limited number of subjects receiving K56 (N=45 subjects). This does not allow a robust comparison of data from this regimen to data from the K27 regimen. Statistical models will be used to determine a favorable or unfavorable association of clinical parameters and choice of carfilzomib regimen.

- Research Question and Objectives

Objectives	Endpoints
Primary	

 • Describe the benefit-risk profile for each pre-specified K regimen (K27, Kd27, K56, Kd56) based on the clinical parameters that are associated with efficacy and safety outcomes from the pooled data meeting the criteria for sample size and completeness of covariates 	
 • Efficacy outcomes: Progression free survival (PFS) and Objective Response • Safety outcomes: 
 ○ Grade 3 or higher adverse events and Serious Adverse Events (SAE) for the following key risks that may impact the overall benefit risk profile of carfilzomib: 
 ▪ Cardiac failure (SMQN) ▪ Acute Renal failure (SMQN) ▪ Hypertension (SMQN) ▪ Cardiac events [totaling the incidence using cardiac failure (SMQN), ischaemic heart disease (SMQN), torsades des pointes including QT prolongation (SMQN)] ○ Fatal adverse events
Secondary	

 • Compare efficacy and safety outcomes for K dosing regimens with dexamethasone (Kd27 versus Kd56) 	
 • Same efficacy and safety endpoints in the primary objective
Exploratory	

 • Compare efficacy and safety outcomes for K27 dosing regimens without and with dexamethasone (K27 versus Kd27) 	
 • Same efficacy and safety endpoints in the primary objective

- Hypothesis(es)/Estimation

No formal hypothesis testing is planned for the efficacy and safety comparison between K dosing regimens (Kd56 versus Kd27; Kd27 versus K27). All analyses will be descriptive.

- Study Design/Type

This is a retrospective, post-hoc, pooled analysis of interventional carfilzomib studies using internal data from Onyx-owned databases and the RAVE database, which is used for all clinical trials conducted by Amgen that span across the globe.

- Study Population or Data Resource

The study population is all subjects with relapsed or refractory relapsed multiple myeloma (RRMM) who received consistent twice-weekly K treatment with K27, Kd27, K56, or Kd56 via an Amgen-sponsored clinical trial.

- Summary of Eligibility Criteria

- Amgen acquired or sponsored clinical trial
- Clinical trial that enrolled subjects with RRMM
- Subjects treated with K administered as twice weekly in the following regimens: K27, Kd27, K56, or Kd56

- Variables

Selection of current treatments depend on a plethora of clinical parameters that vary in important and might affect the choice of K regimen for a particular patient. Given that the benefit-risk assessment is a cornerstone of decision making in medicine, and benefit-risk assessment is based upon efficacy outcomes and safety outcomes ([Reaney et al, 2019](#); [Curtin et al, 2011](#)), special consideration will be given to clinical parameters known to impact efficacy and safety outcomes in those treated with carfilzomib. Specified below are the clinical parameters for analysis ([List 1](#)) for efficacy outcomes such as progression-free survival (PFS) and objective response rate and safety outcomes such as fatalities, grade 3 or higher AEs of special interest for carfilzomib, and serious AEs of special interest for carfilzomib. Variables common to both efficacy and safety outcomes are listed first.

List 1. Planned Variables to be Analyzed that May Inform the Choice of Carfilzomib Dosing Regimen

Variables for efficacy outcomes	Variables for safety outcomes
Age	Age
Gender	Gender
Race	Race
Ethnicity	Ethnicity
Body mass index	Body mass index
ECOG* performance status	ECOG performance status
Creatinine clearance	Creatinine clearance
Time from initial diagnosis	Diabetes
Stage of disease (International Staging System)	Dyslipidemia/hypercholesterolemia

Lactate dehydrogenase	Hypertension
Presence of plasmacytoma	Left ventricular hypertrophy
Number of prior lines of therapy	Chronic kidney disease
Prior stem cell transplant	Coronary artery disease
Prior exposure to lenalidomide	Year of treatment initiation
Prior exposure to bortezomib	
Refractory to lenalidomide	
Refractory to bortezomib	
Refractory to last treatment	
Time from last relapse or last treatment	
Year of treatment initiation	

* Eastern Cooperative Oncology Group

- Study Sample Size

For the carfilzomib regimens K27, K56, Kd27, and K56, the approximate number of subjects for the pooled analysis are 559, 45, 586, and 627 respectively from 13 different Amgen-sponsored clinical trials. The sample size is based on the eligibility criteria.

- Data Analysis

In response to the anticipated variations in the sample sizes and data variables collected for these clinical trials, there will be a primary analysis to avoid the introduction of extra-variation to the pooled data and a subsequent sensitivity analysis. The primary analysis will consist of all studies that meet the eligibility criteria with an adequate sample size of at least 20 subjects and at least 80% completeness of data for each variable in [List 1](#). The subsequent sensitivity analysis will consist of all studies that meet the eligibility criteria.

5. Rationale and Background

5.1 Diseases and Therapeutic Area

Multiple myeloma is the second most common hematological malignancy with more than 150,000 new diagnoses per year globally ([Bray et al, 2018](#)). Certain populations are at higher risk of developing MM, namely the elderly with the peak number of new diagnoses in individuals aged 65 to 74 years. African Americans are twice as likely to develop MM than Caucasian-Americans. Men are slightly more likely to develop MM compared to women ([Ailawadhi et al, 2019](#)). As the most common malignant plasma cell disorder, MM is characterized by neoplastic proliferation of a predominant clone of plasma cells that produce a monoclonal immunoglobulin protein. Each person with MM

tends to harbor subclones of plasma cells, which can evolve and mutate. This genetic heterogeneity of abnormal plasma cells is hypothesized to drive disease progression and treatment resistance. As a result, MM is characterized by periods of remission and relapse, but remains ultimately fatal ([Durie, 2018](#)).

The introduction of novel treatment agents has revolutionized the treatment landscape such that the median survival now extends to approximately 5 years ([SEER Database 2010-2016](#)). One of the novel treatment agents is K, a second-generation proteasome inhibitor (PI) that the FDA granted accelerated approval in 2012 for use in individuals with RRMM. Phase 1 studies with K noted better tolerance when administered 2 consecutive days at the start of each week for three weeks of each four-week cycle compared to 5 consecutive days at the start of each two-week cycle. As monotherapy, K at a dose of 27mg/m² demonstrated efficacy. The absence of a maximally tolerated dose led to subsequent escalation studies, which suggested improved efficacy without significant additional toxicity at a dose of 56mg/m² when infused over a duration of 30 minutes instead of 10 minutes, a regimen which was also approved by the FDA. When combined with the therapeutic dose for dexamethasone, Kd demonstrated improved efficacy with a comparable safety profile to previous phase 1 and 2 trials. It was the pivotal phase 3 ENDEAVOR clinical trial that established K 20/56 with dexamethasone (Kd 20/56) as a cornerstone for treatment in RRMM ([O'Connor et al, 2009](#); [Packet insert for Kyprolis, 2019](#); [Goren et al, 2019](#)).

Interest in identifying the optimal dosing for K as monotherapy or in combination with other agents has sparked several clinical trials, including the SWOG-sponsored S1304 clinical trial (NCT02159848). However, prior attempts to evaluate different K and Kd dosing regimens demonstrated limitations of the collected data on clinical variables and outcomes.

5.2 Rationale

Given the anticipated limitations from other investigator-sponsored studies, only Amgen-sponsored K clinical trials at any phase in the RRMM setting will be reviewed for this pooled analysis. The aim of this post-hoc analysis pooled from Amgen-sponsored clinical trials is to describe the benefit-risk profile of clinical parameters associated with efficacy and safety outcomes of subjects treated with K27, Kd27, K56, or Kd56 to inform the choice of carfilzomib regimen.

5.3 Feasibility and Futility Considerations

Upon initial review of Amgen-sponsored K clinical trials, there was limited data for K56 (N=45 subjects) and does not allow for a robust comparison of data from this regimen to data from the K27 regimen. Statistical models will be used to determine a favorable or unfavorable association of clinical parameters and choice of carfilzomib regimen.

5.4 Statistical Inference

This study is descriptive in nature and will not test any hypotheses.

6. Research Question and Objectives

6.1 Primary

Describe the benefit-risk profile for each pre-specified K regimen (K27, Kd27, K56, Kd56) based on the clinical parameters that are associated with efficacy and safety outcomes from the pooled data meeting the criteria for sample size and completeness of covariates

6.2 Secondary

Compare efficacy and safety outcomes for K dosing regimens with dexamethasone (Kd27 versus Kd56)

6.3 Exploratory

Compare efficacy and safety outcomes for K27 dosing regimens without and with dexamethasone (K27 versus Kd27)

7. Research Methods

7.1 Study Design

This is a retrospective cohort study using the data entered Onyx-owned databases and Amgen RAVE database, which is used for all clinical trials conducted by Amgen.

7.2 Setting and Study Population

Eligible subjects will be derived from clinical trials that have yielded data as of 14 July 2019, when drafting of this protocol and corresponding statistical analysis plan began.

7.2.1 Subject Eligibility

7.2.1.1 Inclusion Criteria

Step 1: Identify all Amgen acquired or sponsored studies in Onyx-owned or RAVE database until 14 July 2019.

Step 2: Within those databases, identify all clinical studies that enrolled subjects with RRMM

- These subjects may have received any number of prior lines of therapy

Step 3: Among those clinical studies, identify all subjects treated with K dosing frequency of twice a week at the start of each week for three of the four-week cycles (days 1, 2, 8, 9, 15, 16 for each 28-day cycle) for all cycles of treatment.

Step 4: Separate these subjects based on treatment of K27, Kd27, K56, or Kd56. If the regimen in the individual clinical trial dictates that the first and/or second cycle of K therapy is 15mg/m² or 20mg/m², but 27mg/m² is specified for subsequent K cycles of therapy, then the clinical trial will be included for subjects who receive K at 27mg/m² with or without dexamethasone.

- If the regimen in the clinical trial dictates that the first cycle of K therapy is 27mg/m², but 56mg/m² is specified for subsequent K cycles of therapy, then the clinical trial will be included for subjects who receive K at 56 mg/m² with or without dexamethasone.
- Therapeutic dexamethasone dosing will be based on the subject receiving at least 20mg per week.

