ALL = acute lymphoblastic leukemia; AUC = area under the concentration-time curve; BIW = twice weekly; BTZ = bortezomib; CFZ = carfilzomib; C-MAP = Carfilzomib Multiple Myeloma Expanded Access Protocol; CrCL = creatinine clearance; CYC = cyclophosphamide; Dara = daratumumab; DDI = drug-drug interaction; DEX = dexamethasone; ESRD = end-stage renal disease; HD = Hodgkin's disease; LEN = lenalidomide; MEL = melphalan; Mito = mitoxantrone; MM = multiple myeloma; MTD = maximum tolerated dose; NHL = non-Hodgkin's lymphoma; PDn = pharmacodynamics; PEG = polyethylene glycol; PK = pharmacokinetics; POM = pomalidomide; PRED = prednisone; QD = once daily; QTc = corrected QT interval; QW = once weekly; R3 = dexamethasone, mitoxantrone, PEG-asparaginase, and vincristine; SCLC = small-cell lung cancer; tx = therapy(ies); US = United States; VCR = vincristine; VXLD = vincristine, dexamethasone, PEG-asparaginase, and daunorubicin; WM = Waldenström's macroglobulinemia
 Studies 2011-003 (ENDEAVOR) and 2012-005 (CLARION) are co-sponsored by Amgen and Ono Pharmaceutical Co, Ltd. in Japan and is sponsored solely by Amgen in other participating countries. All other studies are sponsored solely by Amgen.
 All studies were open-label.

^aUnless otherwise noted, carfilzomib was administered in 28-day cycles on days 1, 2, 8, 9, 15, and 16 until progressive disease. Stepped-up dosing was allowed on cycle 1 day 8 for Studies PX-171-009 (ASPIRE), PX-171-011 (FOCUS), 2011-003 (ENDEAVOR), PX-171-007, 2011-002, CFZ001, CFZ002, 20140242 (CFZ005), 20140355 (A.R.R.O.W.), 20160275 (CANDOR); on cycle 2 day 1 for Studies PX-171-002 – Part 2, PX-171-003 – Part 2 (A1), PX-171-004 – Part 2, and PX-171-005. Where applicable, and unless otherwise noted, dexamethasone was administered at 40 mg weekly.

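### Cohort entry depends on dose, schedule and dexamethasone received after baseline, and the step-up day differs by trial, so early failures are removed more from K27 than from Kd27

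*Protocol*

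**What the plan says.** Protocol Section 7.2.1.1, Step 3 takes subjects treated twice weekly, "days 1, 2, 8, 9, 15, 16 for each 28-day cycle) for all cycles of treatment". Step 4 screens each trial on the regimen it specifies and adds, for the lower dose, "then the clinical trial will be included for subjects who receive K at 27mg/m² with or without dexamethasone", with parallel wording for the higher dose: "then the clinical trial will be included for subjects who receive K at 56 mg/m² with or without dexamethasone". K is separated from Kd by treatment received: "Therapeutic dexamethasone dosing will be based on the subject receiving at least 20mg per week". The Abstract describes the population as subjects "who received consistent twice-weekly K treatment with K27, Kd27, K56, or Kd56".

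Section 7.2.3 ends baseline before the first dose of protocol treatment. Section 7.7.2.3 counts treatment duration from the first carfilzomib dose.

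Table 1 footnote a gives two step-up times. For ten studies, including FOCUS, 2011-002, CFZ005, A.R.R.O.W., ENDEAVOR and CANDOR: "Stepped-up dosing was allowed on cycle 1 day 8 for Studies". For PX-171-002, -003, -004 (Part 2 of each) and PX-171-005 it is "on cycle 2 day 1 for Studies PX-171-002" onward in the list, which is day 29 of 28-day cycles. Step 4 itself speaks of a lower dose for the first and possibly second cycle, which does not match a step-up on day 8 of cycle 1.

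**The concern.** Selecting on something that happens after time zero creates guaranteed survival time. If a subject must receive the target dose to be counted, anyone who dies, progresses or stops before step-up is left out, while time for everyone else still runs from the first dose. When the wait is one week in some trials and four in others, and the four-week trials sit mostly in one regimen, the comparison is distorted even if the regimens are equivalent.

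Nothing in the protocol corrects this. The propensity model in Section 7.2.2 uses List 1 covariates, all measured at baseline, so it cannot undo selection on later treatment. Guaranteed time also lengthens exposure in the denominators of the exposure-adjusted incidence rates. Sections 7.9.1.1 to 7.9.3 do not mention the issue. The ENCePP checklist answers yes on information bias, with time-related bias among its examples, and cites Section 7.3.4, which deals only with calendar year of treatment initiation.

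The results at stake are PFS, response, fatal events and serious or grade 3+ events in each regimen's primary profile, chiefly K27, and the exploratory K27 versus Kd27 comparison. The report goes to a regulator (Section 11).

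**Working it through.** **1. Reproduce the totals in Table 2.**
- K27: 78 + 200 + 157 + 105 = 540
- Kd27: 235 + 123 + 20 + 205 = 583
- Kd56: 153 + 463 = 616

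All agree with the protocol.

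**2. Tag each trial by the step-up day in footnote a.** Day 29 applies to 20140118 (PX-171-003), 20140119 (PX-171-004) and 20140120 (PX-171-005). The others in these three columns step up on day 8.
- K27: (200 + 78)/540 = 278/540 = 51.5% on day 29; 262/540 = 48.5% on day 8
- Kd27: 20/583 = 3.4% on day 29; 563/583 = 96.6% on day 8
- Kd56: 0/616 on day 29

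The sensitivity set (Table 3) is similar. K27 is (7 + 8 + 78 + 200)/559 = 293/559 = 52.4%, Kd27 is (3 + 20)/586 = 23/586 = 3.9%, and Kd56 is 0/627.

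**3. Mean time a subject must stay on treatment to qualify, if receipt is required.**
- K27: (28×278 + 7×262)/540 = 9618/540 = 17.8 days
- Kd27: (28×20 + 7×563)/583 = 4501/583 = 7.7 days
- Kd56: 7.0 days

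**4. Does the document sort by treatment received?** CFZ001, planned as 20/27/56, supplies 4 subjects to K27, 19 to K56 and 3 to Kd56. Its listed dexamethasone is 8 mg twice weekly, 16 mg per week, below the 20 mg threshold, yet 3 subjects are Kd56. The single-arm study 2011-002 is split into 105 K27 and 205 Kd27. A purely planned-regimen rule does not readily produce these splits.

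**5. Illustrative size.** The protocol gives no PFS figures. Assumptions: exponential PFS with median m months, true hazard ratio 1, clock from first dose, entry only if event-free to the step-up day, follow-up cut at 18 months.

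Let F(t) = 1 − exp(−ln 2 × t/(30.4375 m)), and let p be the day-29 share among subjects who entered. The share of the starting cohort lost before step-up is 1 − 1/[p/(1 − F(28)) + (1 − p)/(1 − F(7))].

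For K27 at m = 3: F(7) = 0.052, F(28) = 0.191, and 1 − 1/(0.515/0.809 + 0.485/0.948) = 12.9%.

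| Median PFS (months) | Lost, K27 | Lost, Kd27 | HR K27/Kd27 |
|---|---|---|---|
| 3 | 12.9% | 5.7% | 0.93 |
| 4 | 9.8% | 4.3% | 0.94 |
| 6 | 6.6% | 2.9% | 0.96 |
| 9 | 4.4% | 1.9% | 0.97 |
| 12 | 3.3% | 1.5% | 0.97 |

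The hazard ratios solve the large-sample Cox score equation. Simulations of the same model, with their noise, ran from 0.92 to 0.97. The K27 median comes out about 10 days longer. For Kd56 versus Kd27 the hazard ratio is 1.00 to 1.01.

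**6. Possible offset.** 2011-002 and PX-171-005 list carfilzomib alone in the Table 1 drug column, yet supply 205 + 20 = 225 of 583 Kd27 subjects (38.6%). If these subjects count as Kd only once dexamethasone was given, they too had to remain on treatment until then. The protocol gives no timing, so this cannot be sized.

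**The case against.** The best defence is that Step 4 is a trial-level rule. It asks what the trial specifies, and the words about subjects receiving a dose may only name the cohort that the trial feeds. No enrolled or treated denominators are given, so no count can be shown to be short, and the SAP may hold the subject-level rule. CFZ001, the clearest sign of sorting by dose received, is not in the K27 primary set, and its 4 subjects were moved to K27, not deleted. This shows that the text is ambiguous. It does not rescue it: Section 7.7.2.3.1 enrols by these criteria, and the within-trial splits fit sorting by receipt better.

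Some stronger conclusions are tempting but not supported:
- A reader might infer that early failures vanish from K27 only. They do not: 48.5% of K27 steps up on day 8, and Kd27 loses its own failures before day 8 and has 20 late-step-up subjects.
- A reader might infer that the all-cycles clause removes early failures. A subject who stops in cycle 1 kept the schedule for every cycle received; the clause removes subjects whose schedule was changed.
- A reader might infer that half of K27 is guaranteed free of events in cycle 1. Reaching step-up rules out death and discontinuation, not a grade 3+ or serious event after which treatment continued.
- A reader might want a figure for understated fatal events. The protocol gives no timing of deaths, so none can be supported.
- A reader might take the bias as certain to favour K27. The dexamethasone rule may work the other way.

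It is also fair that all analyses are descriptive and that the illustrated shift is modest for a non-randomised cross-trial comparison.

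**Conclusion.** The concern stands as a defect in the inclusion criteria. As written, membership rests on post-baseline dose, schedule and dexamethasone. The day-29 condition falls on 51.5% of K27, 3.4% of Kd27 and none of Kd56. If receipt of the target dose is required, early failures are removed more from K27 than from Kd27, with a spurious hazard ratio of about 0.92 to 0.97 under the stated assumptions. The shares come from the protocol's own counts; the hazard ratio does not and is only an illustration. The net direction is uncertain because of the dexamethasone rule. The schedule clause is a separate selection that acts in every regimen. The secondary Kd27 versus Kd56 comparison is little affected by step-up day.

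**What to change.** 1. Assign carfilzomib cohorts by the regimen planned or assigned in the trial or arm. Include every subject with at least one carfilzomib dose, from that dose, whatever happens later to dose or schedule.
2. Remove the all-cycles clause of Step 3 and the receipt wording of Step 4 as subject-level entry conditions.
3. Where the trial plan does not fix dexamethasone (for example 2011-002 and PX-171-005), assign K or Kd from information at or near treatment start, by one rule for both groups.
4. Add a sensitivity analysis of K27 versus Kd27 with a common day-29 landmark: keep subjects still at risk on day 29 in both groups and start the clock there.
5. Reconcile Step 4's first-and/or-second-cycle wording with the step-up days in footnote a.
6. Update Tables 1 to 3.

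The data are already held. The cost is rewording, re-selection and new counts. Some trial-by-regimen cells may cross the 20-subject threshold for the primary set, since PX-171-005 supplies exactly 20 Kd27 subjects and CFZ001 supplies 19 K56 subjects. The cohorts will also contain some subjects who never reached the target dose; the exposure summaries in Section 7.7.2.3 can show how many.

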7.2.1.2 Exclusion Criteria

Exclude any subjects duplicated among the different carfilzomib regimens

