20140120 (PX-171-005)	Phase 2 Study of the Safety and Pharmacokinetics of carfilzomib in Subjects with relapsed and Refractory Multiple Myeloma and Varying Degrees of Renal Function	Relapsed and refractory MM; ≥ 2 prior tx; varying degrees of renal function	Phase 2, single arm, parallel cohorts by CrCL grouping	PK; safety and tolerability; PDn; QTc; efficacy	Carfilzomib 15/20/27 mg/m ² (2 to 10 min)	K27: 8 subjects Kd27: 20 subjects

Footnotes defined on last page of the table

Table 1. Summary of Individual Clinical Trials to Derive Subject Data for Pooled Analysis

Study Number	Study Title	Subject Population	Design	Objectives	Drug Combination/ K Dose Schedule ^a	Eligible Subjects (K regimen: subject #)
20140119 (PX-171-004 – Part 1 and Part 2)	An Open-label, Single-arm, Phase 2 Study of Carfilzomib in Patients with Relapsed and Refractory Multiple Myeloma	Relapsed or refractory MM; 1 to 3 prior tx	Phase 2 Part 1: single arm Part 2: 2 dosing cohorts	Safety; efficacy; PK	Carfilzomib Part 1: 20 mg/m ² (10 min) Part 2: 20 or 20/27 mg/m ² (10 min) up to 12 cycles	K27: 78 subjects
20140118 (PX-171-003 – Part 1 (A0) and Part 2 (A1))	An Open-label, Single-arm, Phase 2 Study of Carfilzomib in Patients with Relapsed and Refractory Multiple Myeloma	Relapsed and refractory MM; ≥ 2 prior tx	Phase 2, single arm	Efficacy; safety; PK; PDn	Carfilzomib Part 1: 20 mg/m ² (2 min) Part 2: 20/27 mg/m ² (10 min) up to 12 cycles	K27: 200 subjects
20130402 (CFZ002)	An Open-label, Single Arm, Phase 1 Study of the Pharmacokinetics and Safety of Carfilzomib in Subjects with Advanced malignancies and varying Degrees of Hepatic Impairment	Relapsed or progressive advanced malignancies; ≥ 2 prior tx; varying degrees of hepatic function	Phase 1, comparative PK with 4 cohorts based on liver function	Assess hepatic impairment on AUC	Carfilzomib + dexamethasone K 20/27/56 mg/m ² (30 min) dex 8 mg BIW	K56: 2 subjects

Footnotes defined on last page of the table

Table 1. Summary of Individual Clinical Trials to Derive Subject Data for Pooled Analysis

Study Number	Study Title	Subject Population	Design	Objectives	Drug Combination/ K Dose Schedule ^a	Eligible Subjects (K regimen: subject #)

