20130401 (CFZ001)	An Open-label, Single Arm, Phase 1 Study of the Pharmacokinetics and Safety of Carfilzomib in Subjects with Relapsed Multiple Myeloma and End-stage Renal Disease	Relapsed or refractory MM; ≥ 1 prior tx; normal renal function or ESRD on hemodialysis	Phase 1, comparative PK with 2 cohorts based on CrCL	Assess influence of ESRD on AUC	Carfilzomib + dexamethasone K 20/27/56 mg/m ² (30 min) dex 8 mg BIW	K27: 4 subjects K56: 19 subjects Kd56: 3 subjects
20130398 (2011-003)	A Randomized, Open-label, Phase 3 Study of Carfilzomib Plus Dexamethasone Versus Bortezomib Plus Dexamethasone in Patients With Relapsed Multiple Myeloma (ENDEAVOR)	Relapsed MM; 1 to 3 prior tx	Phase 3, randomized, active-control	Efficacy; safety	Carfilzomib + dexamethasone vs bortezomib (V) + dexamethasone K 20/56 mg/m ² (30 min) dex 20 mg V 1.3 mg/m ²	Kd56: 463 subjects
20130396 (PX-171-011)	A Randomized, Open-label, Phase 3 Study of Carfilzomib vs Best Supportive Care in Subjects with Relapsed and Refractory Multiple Myeloma (FOCUS)	Relapsed and refractory MM; ≥ 3 prior tx	Phase 3, randomized, active-control	Efficacy; safety	Carfilzomib vs best supportive care K 20/27 mg/m ² (10 min) Corticosteroid (prednisolone 30 mg or dex 6 mg every other day) Optional CYC 50 mg QD	K27: 157 subjects

Footnotes defined on next page of the table

Table 1. Summary of Individual Clinical Trials to Derive Subject Data for Pooled Analysis

Study Number	Study Title	Subject Population	Design	Objectives	Drug Combination/ K Dose Schedule ^a	Eligible Subjects (K regimen: subject #)
20130393 (PX-171-007)	Phase 1b/2, Multicenter Open-label Study of the Safety and Activity of Carfilzomib in subjects with Relapsed Solids Tumors, Multiple Myeloma, or Lymphoma	Relapsed or refractory MM; ≥ 2 prior tx	Phase 1b/2, dose escalation	Safety and tolerability	Carfilzomib 20/36 to 20/70 mg/m ² (30 min)	K56: 24 subjects Kd56: 8 subjects
					Carfilzomib + dexamethasone K 20/45 or 20/56 mg/m ² (30 min)	
2011-002	Carfilzomib Multiple Myeloma Expanded Access protocol (C-MAP) for Subjects with Relapsed and Refractory Disease (C-MAP)	Relapsed or refractory MM; ≥ 4 prior tx; unable to enroll in another US CFZ study	Phase 2, single arm; expanded access program	Safety	Carfilzomib 20/27 mg/m ² (10 min)	K27: 105 subjects Kd27: 205 subjects

Page 5 of 5

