7.7.1.1 Primary Analysis

In response to the anticipated variations in the sample sizes and data variables collected for these 13 clinical trials, there will be a primary analysis and a subsequent sensitivity analysis to avoid the introduction of extra-variation to the pooled data. The primary analysis will consist of all studies that meet the eligibility criteria with an adequate sample size of at least 20 subjects and at least 80% completeness of data for each variable in [List 1](#) (Table 2). This yields 5 clinical trials for K monotherapy totaling 564 subjects and 6 clinical trials for Kd totaling 1,199 subjects.

Table 2. Clinical Trials for Primary Data Analysis

K27 (540 subjects)	K56 (24 subjects)	Kd27 (583 subjects)	Kd56 (616 subjects)
20140119 (78 subjects)	20130393 (24 subjects)	20140355 (235 subjects)	20160275 (153 subjects)
20140118 (200 subjects)		20140242 (123 subjects)	20130398 (463 subjects)
20130396 (157 subjects)		20140120 (20 subjects)	
2011-002 (105 subjects)		2011-002 (205 subjects)	

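### The K/Kd label rests on dexamethasone received, with no time anchor, so up to 39% of primary-set Kd27 subjects may be labelled by post-baseline behaviour

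*Protocol*

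**What the plan says.** Protocol 7.2.1.1, Step 4, sorts subjects into K27, Kd27, K56 and Kd56. The only rule on dexamethasone is "Therapeutic dexamethasone dosing will be based on the subject receiving at least 20mg per week". The only exclusion criterion (7.2.1.2) is "Exclude any subjects duplicated among the different carfilzomib regimens".

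Table 1 (7.7.1) gives the counts. For 2011-002, a single-arm expanded-access study listed as carfilzomib alone, it reports "K27: 105 subjects Kd27: 205 subjects". For 20140120, a single-arm study with cohorts by creatinine clearance and also listed as carfilzomib alone, it reports "K27: 8 subjects Kd27: 20 subjects".

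Nothing else in the protocol dates the label. The baseline period (7.2.3) governs List 1 covariates, and the exposure definitions (7.7.2.3) cover carfilzomib only. The checklist in Appendix A marks exposure time windows (item 5.3) as not applicable. For information bias, including time-related bias (item 7.3), it cites only 7.3.4, the year of treatment initiation. The propensity model (7.2.2) uses List 1, which holds nothing on dexamethasone timing.

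**The concern.** Group membership in a cohort comparison should be knowable at time zero. If a subject counts as Kd27 because dexamethasone was added in a later cycle, that subject had to stay on treatment until then. A subject who progressed or died first stays K27. The time before the addition is then credited to Kd27 for PFS, for fatal events and in the exposure-adjusted rates of 7.7.2.4. If dexamethasone was added because response was poor, the label also carries prognostic information gained after baseline. Balancing baseline covariates cannot undo either effect.

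The contrast most exposed is the exploratory K27 versus Kd27. The same labels also supply the Kd27 side of the secondary Kd27 versus Kd56 comparison and the per-regimen profiles of the primary objective. The report is to go to a regulator (section 11) and is meant to inform the choice of regimen.

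**Working it through.** **1. Reproduce the plan's totals (Tables 2 and 3).**
- Primary Kd27: 235 + 123 + 20 + 205 = 583. Primary K27: 78 + 200 + 157 + 105 = 540.
- Sensitivity Kd27: 235 + 123 + 3 + 20 + 205 = 586.

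All agree with the protocol.

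**2. Find the trials whose split cannot come from an assigned regimen (Table 1).**

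| Trial | Regimen listed | Labels given |
|---|---|---|
| 2011-002 | carfilzomib alone, single arm | 105 K27, 205 Kd27 |
| 20140120 | carfilzomib alone, single arm | 8 K27, 20 Kd27 (only the 20 enter the primary set) |
| 20140122 | carfilzomib alone, dose escalation | 7 K27, 3 Kd27 (sensitivity set only) |
| 20130401 | with dexamethasone 8 mg twice weekly | 4 K27, 19 K56, 3 Kd56 (sensitivity set only) |

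The last row is informative. Two doses of 8 mg make 16 mg per week, below the threshold, so no subject would be Kd on the listed regimen, yet 3 are. Among the rules shown, only subject-level receipt could produce these splits.

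**3. Share of each pool exposed.**
- Kd27, primary: (205 + 20)/583 = 225/583 = 38.6%.
- Kd27, sensitivity: (205 + 20 + 3)/586 = 228/586 = 38.9%.
- K27, primary: 105/540 = 19.4%.
- Both primary pools: (225 + 105)/(540 + 583) = 330/1,123 = 29.4%.

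The other 583 − 225 = 358 Kd27 subjects come from trials whose own regimen includes dexamethasone.

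**4. Dependence on 2011-002 for PFS.** If that study supplies no PFS data, the exposed Kd27 share for PFS falls to 20/(583 − 205) = 20/378 = 5.3%. Its safety data stay exposed.

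**5. What late starts could do to a PFS hazard ratio (illustration only).** None of these inputs is in the protocol: no true dexamethasone effect, exponential PFS with median 4 or 8 months, Cox model, censoring at 24 months, and dexamethasone added at random during treatment. The mixed trials hold 330 subjects; 358 Kd27 and 435 K27 subjects come from the other trials.

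| Share of mixed-trial Kd27 labels due to later starts | HR within mixed trials | HR in whole pool |
|---|---|---|
| 0% | 1.0 | 1.0 |
| 10% | 0.74–0.79 | 0.92–0.96 |
| 25% | 0.54–0.56 | 0.87–0.89 |
| 50% | 0.36 | 0.80–0.83 |

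A second set of assumptions used median PFS of 3 to 6 months, censoring at 18 months, and 10%, 25% or 50% of the 205 due to start 1 to 3 months after entry, with those who fail first counted as K27. It gives pooled values of about 0.97, 0.91–0.95 and 0.84–0.91. Neither set applies the planned caliper matching, so neither estimates the planned contrast.

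**6. Without the two trials.** Kd27 = 235 + 123 = 358 and K27 = 78 + 200 + 157 = 435. In the primary set only 2011-002 supplies both groups (310 of 1,123, 27.6%), so after its removal no trial does.

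**The case against.** The strongest reply is that the mechanism is inferred. Step 4 sets a dose threshold and is silent on timing. Table 1 is a summary, and its footnote gives a weekly dexamethasone dose where applicable. Subjects in the two trials may all have begun dexamethasone with carfilzomib, in which case this bias is nil. That stands: 39% is an upper bound.

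A reader might infer that the bias favours Kd27. The documents do not support a fixed direction. Later addition credits survival time to Kd27, but addition for poor response would usually work against it. A rule based on average weekly dose could move long-treated subjects with dose reductions into K27. The illustration above models only later addition at random.

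A reader might also infer a distorted PFS result from 2011-002. Table 1 gives that study a safety objective only, and the 80% completeness rule covers List 1 variables, not outcomes. Its PFS contribution is therefore uncertain.

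The exclusion of duplicated subjects may only prevent double counting. If it does remove late starters, they are not in Kd27 and the illustrated mechanism does not operate; selection on a later event takes its place.

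Finally, the statistical analysis plan is not at hand and may set a window, and the contrast is exploratory and descriptive. This lowers the severity but does not dispose of the point. The protocol itself states the group-defining rule, reports counts by regimen and marks time windows as not applicable.

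**Conclusion.** The concern holds in conditional form. The K/Kd label is defined by receipt without a time anchor. Up to 225 of 583 primary-set Kd27 subjects (38.6%) and 105 of 540 K27 subjects (19.4%) may owe their label to what happened after the first dose. This rests on reading Table 1 as listing those two trials' regimens completely.

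It would go too far to say that 39% are mislabelled, that Kd27 is favoured, or that any hazard ratio above is the expected error. The share of late starters is not stated, the direction depends on why dexamethasone was added and how the threshold is averaged, and the simulation inputs are assumptions. For 2011-002 the effect may fall mainly on safety outcomes, and no safety effect has been quantified. Nor has any bias been quantified for Kd27 versus Kd56 or for the per-regimen descriptions, which use the same labels.

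This should be fixed; confidence is moderate.

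**What to change.** - In Step 4, keep the existing threshold but assess the K/Kd label at treatment start: dexamethasone assigned, or begun with the first carfilzomib dose. Keep later starters and stoppers in the group they began in.
- In 7.2.1.2, state that the duplicate exclusion does not remove subjects for a later switch.
- Re-run the classification and update the counts in Tables 1 to 3.
- Add a sensitivity analysis of K27 versus Kd27 without 2011-002 and 20140120. On present counts this is 435 versus 358 before matching. State that in the primary set no trial then contributes to both groups, so regimen and trial cannot be separated.

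The cost is a change of wording in the protocol and its analysis plan and one re-run of the classification, with some subjects possibly changing group. It needs dexamethasone start dates for the mixed trials; the protocol does not say whether these are held, so their availability should be confirmed first.
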